### 2.3. Study Design

Overview of Study Design and Key Features	

Up to 30 Days Before Visit 2 (i.e. up to 30 days prior to start of baseline assessments)
 
Rescue Medication Baseline use to include MDI sensor and daily diary
 
Follow up visit to occur within 28 days of last dose of study treatment
	
Design Features	This is a parallel group, randomized, double-blind (sponsor open), placebo-controlled, multi-centre, dose ranging study.
Dosing	Study treatment will be administered twice daily for 24 weeks.
Time & Events	Refer to Appendix 2: Schedule of Activities
Treatment Assignment	Participants will be randomized (1:1:1:1:1) to receive one of five dose strengths of danirixin (5 mg, 10 mg, 25 mg, 35 mg and 50 mg) or placebo. Randomization was stratified by smoking status.
Interim Analysis	
Three specific interim analyses were defined for the study, with the protocol allowing for additional administrative interims as required.
 
An administrative interim was performed in October 2017 and included plots of E-RS: COPD total score (and subscale scores) over time by treatment, to aid internal decision-making on the project.
 
The first protocol specified interim analysis was an evaluation of danirixin PK after 10 participants in each treatment group had completed Visit 3

Overview of Study Design and Key Features	
	
(Day 1). This analysis was performed in December 2017.
 
A protocol specified futility interim analysis based on the E-RS: COPD endpoint was conducted after approximately 150 participants had completed 3 months of study treatment. This analysis was performed in February 2018.
 
A further protocol specified strategic interim analysis will be conducted when approximately 450 participants have completed 6 months of treatment. This strategic interim will be used to support GlaxoSmithKline (GSK) decisions regarding additional investment and further development of danirixin. It will include endpoints as specified in Section 2.2 and in the list of data displays in Appendix 11. No changes will be made to the study based on the results of this strategic interim analysis unless a safety concern is identified.
 
Outputs containing unblinded treatment assignments will be created for all interim analyses and will only be made available to a limited number of GSK staff. Full details will be included in the study results dissemination plan (SRDP).

## 2.4. Statistical Hypotheses

The primary efficacy endpoint is the change from baseline of E-RS: COPD total score at Month 6. The primary objective of the study is to characterize the dose response of danirixin and select appropriate dose(s) for future drug development.

A model based probability inference approach in Bayesian framework will be used to guide decision-making around dose selection. The posterior probability that the change from baseline of E-RS: COPD total score for each active dose is less than placebo will be derived.

No formal statistical hypothesis will be tested in the primary efficacy analysis.

### **3. PLANNED ANALYSES**

#### **3.1. Interim Analyses**

##### **3.1.1. Interim PK Analysis**

After approximately 10 participants in the PK subset for each treatment group had completed Visit 3 (Day 1), an interim evaluation of danirixin PK parameters was undertaken. The purpose of the interim PK analysis was to determine if danirixin exposures were within the expected range. No formal HARP outputs were produced.

##### **3.1.2. Futility Analysis**

An interim analysis was conducted to allow for the possibility of stopping early for futility after approximately 150 participants had completed 3 months of treatment. This is described in a separate RAP. Outputs featuring unblinded treatment assignments were created and shared with the study team and those listed in the Study Results Dissemination Plan (SRDP).

##### **3.1.3. Strategic Analysis**

When approximately 450 participants had completed 6 months of treatment, a further interim analysis was performed for strategic planning purposes, as described in this RAP. This analysis was planned to be used to aid in the planning of future studies and for a better understanding of benefit/risk profile of danirixin. No changes were made to the study based on the results of this strategic interim analysis.

The analyses were performed after the completion of the following sequential steps:

1. The date of the planned Visit 10 for the 450th completed participant (01AUG2018) had been met.
2. All required database cleaning activities had been completed by Data Management (DM) on data collected up until 01AUG18. Data collected between 02AUG2018 and 5SEP2018 (DBR) for ongoing subjects was not cleaned.
3. Unblinded randomization schedules were released by Randomization coordinator.

Data was reported in System Independent (SI) format. Outputs featuring unblinded treatment assignments were created for this strategic interim analysis, reviewed by the study team and shared with selective GSK personnel (to be included in the SRDP).

##### **3.1.4. Administrative Interims**

Administrative assessments of danirixin exposure, efficacy and spirometry data may be undertaken during the conduct of the study as data becomes available. No decisions regarding study conduct will be made based on these assessments. The reporting team will have access to the unblinded participant treatment assignments. The unblinded study team (as defined in the 205724 Study Charter) will have access to unblinded aggregate data grouped by study treatment assignment.

An administrative interim was performed in October 2017 and included plots of E-RS: COPD total score (and the subgroups) over time by treatment, to aid internal decision-making on the project.

### **3.2. Final Analyses**

The final planned analyses for this Clinical Data Interchange Standards Consortium (CDISC) study will be performed after the completion of the following sequential steps:

1. All participants have completed the study as defined in the protocol.
2. SI data to Study Data Tabulation Model (SDTM) data conversion has been completed by Accenture and quality control (QC) of blinded SDTM has been completed by CDAD and DM. DM will provide the blinded SI PC dataset to Accenture.
3. All required database cleaning activities have been completed and final SI Source Data Lock (SDL) has been declared by DM.
4. Study is unblinded
  - Randomization schedules and container data are released in RANDALL NG.
  - SMS2000 data is released in HARP
5. The SDTMs (including the PK) are unblinded by clinical programming (or representative) using the interim unblinding process.
6. Database freeze (DBF) on unblinded SDTM datasets is declared by DM.

## 4. ANALYSIS POPULATIONS

### 4.1. Strategic Interim Analysis

Population	Definition / Criteria	Analyses Evaluated
All Subjects (ALLSUB)	
 
All participants screened and for whom a record exists on the study database.
 
	
 
Participant disposition
 
Reasons for withdrawal prior to randomization
 
Inclusion/exclusion/randomization criteria deviations for non-randomized participants
 
AEs and SAEs for non-randomized participants
 

Intent-to-treat (ITT)	
 
All randomized participants apart from those who were randomized in error (i.e. were also recorded as screen or run-in failures and did not receive a dose of study treatment).
 
Any participant who receives a treatment randomization number will be considered to have been randomized.
 
Randomized participants will be assumed to have received study medication unless definitive evidence to the contrary exists.
 
Data will be reported according to the randomized treatment.
 
	
 
Selected efficacy displays as described in Section 7
 
Strategic Interim only
 

Modified Intent-To-Treat (mITT)	
 
Same as the Intent-to-treat population, but this population will be 'modified' in that all data summaries and analyses for this population will be based on the actual treatment received, if it is different to the randomized treatment.
 
If any participant received more than one treatment during a treatment period, their data will be reported according to the treatment they received for the longest period of time.
 
	
 
Study Population
 
Safety
 

Per Protocol (PP)	
 
All participants from the mITT population who did not have a protocol deviation considered to impact efficacy
 
	
 
Efficacy
 

Symptomatic	
 
All participants in the PP population who have Chronic Mucus Hypersecretion (CMH) according to baseline SGRQ (see Section 14.6.2) and baseline E-RS: COPD total score (see Section 5.2) <math>\geq 10</math>.
 
	
 
Study Population
 
Selected efficacy displays as described in Section 7
 
Strategic Interim only
 

Refer to [Appendix 11](#): List of Data Displays which details the population used for each display.

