10.4. Populations for Analyses

For purposes of analysis, the following populations are defined:

Population	Description
All Participants	This population will comprise all participants screened and for whom a record exists on the study database and will be used for the tabulation and listing of reasons for withdrawal before randomization and listings of AEs and SAEs for nonrandomized participants.
Modified Intent To Treat (mITT)	
This population will comprise all participants randomized to treatment and who received at least one dose of study medication. Randomized subjects will be assumed to have received study medication unless definitive evidence to the contrary exists. A true Intent-to-treat analysis would use the randomized treatment, but this population will be ‘modified’ in that all data summaries and analyses for this population will be based on the actual treatment received, if it is different to the randomized treatment. This will constitute the primary population for all analyses of efficacy and safety.
 
If any subject received more than one treatment during a treatment period, their data will be reported according to the treatment they received for the longest period of time.

PK	This population will comprise all participants in the mITT population for whom a pharmacokinetic sample was obtained and analyzed while on treatment with DNX.

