10.5.2. Safety Analyses

All safety endpoints will be tabulated or plotted by treatment group and will be performed on the mITT Population. Further details will be described in the RAP.

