## 4.2. Final Analysis

The final analysis will use the same populations as above, plus additional populations as defined below.

Population	Definition / Criteria	Analyses Evaluated
PK	
 
All participants in the mITT population who had at least 1 non-missing PK assessment (Non-quantifiable [NQ] values will be considered as non-missing values) obtained and analysed whilst on treatment with danirixin.
 
	
 
PK
 

PK2	
 
All participants in the PK population who had at least 1 non-missing PK assessment (NQ values will be considered as non-missing values) obtained and analysed whilst on treatment with danirixin from a dry blood spot sample and corresponding wet whole blood sample.
 
	
 
PK Dry Blood Spot vs Wet Whole Blood
 

Refer to [Appendix 11](#): List of Data Displays which details the population used for each display.

In the event one or more investigators are withdrawn from the study due to concerns over protocol deviation then a further population will be defined which will consist of all participants in the PP population excluding participants from those investigative sites. This population will be used to perform additional sensitivity analysis for the primary efficacy endpoint only and will only be defined if the combined enrolment at these sites exceeds  $\geq 2\%$  of the overall PP study enrolment. No other analyses will be repeated.

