## **8. SAFETY ANALYSES**

Details of the planned displays including the population to be used for each display and which displays are produced for the strategic interim are presented in [Appendix 11](#). Additional details are provided below.

The estimand is the effect of actual treatment in the population of participants who were randomized and dosed. All collected data will be included in reporting as described below. Non-recorded missing data following study withdrawal will not be imputed.

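### Read literally, SAP 4.1 omits the protocol's one-dose condition from mITT, so a validly randomised participant who was never dosed would count in the adverse event denominators

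*SAP*

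**What the plan says.** Protocol 10.4 defines mITT as "all participants randomized to treatment and who received at least one dose of study medication", reported by the treatment actually taken. Protocol 10.5.2 makes it the safety set: "All safety endpoints will be tabulated or plotted by treatment group and will be performed on the mITT Population".

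SAP 4.1 builds mITT in two steps. ITT is "All randomized participants apart from those who were randomized in error", and the error group is limited to those who "were also recorded as screen or run-in failures and did not receive a dose of study treatment". mITT is then "Same as the Intent-to-treat population", with data shown by actual treatment where that differs from the randomised one, and it is assigned to the study population and safety displays. The ITT row also says: "Randomized participants will be assumed to have received study medication unless definitive evidence to the contrary exists". SAP 4.2 extends this beyond the strategic interim: "The final analysis will use the same populations as above, plus additional populations as defined below".

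SAP 8 sets the safety estimand in the "population of participants who were randomized and dosed", and SAP 8.4 says the same for spirometry. SAP Table 1, which lists departures from the protocol analysis, records the added populations and the move of efficacy from mITT to per protocol. It has no entry on who belongs to mITT.

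**The concern.** The protocol makes dosing a condition of entry to mITT. The SAP uses it only as one half of an exclusion: being undosed removes a participant only if he or she was also recorded as a screen or run-in failure. Someone eligible and correctly randomised who withdraws before the first tablet meets only one half and is kept.

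Adverse event percentages divide by the arm's mITT count. A person with no exposure belongs to neither the protocol's safety set nor the SAP's stated estimand, yet would be in that count. A programmer who follows the SAP table exactly would build a flag that disagrees with the protocol, and nothing in Table 1 would alert the reader.

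**Working it through.** **Membership.** Let R be randomised, D dosed and F recorded as a screen or run-in failure.

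- Protocol 10.4: mITT = R and D.
- SAP 4.1: mITT = R and not (F and not D).

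| Randomised participant | Protocol mITT | SAP mITT |
|---|---|---|
| Dosed, not F | in | in |
| Dosed, F | in | in |
| Not dosed, F | out | out |
| Not dosed, not F | out | **in** |

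The definitions differ in the last row only. SAP 8 and 8.4 would also leave that row out.

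**Size.** The plan states no figure on this point, so there is none to reproduce. Inputs:

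- Arm size: about 600 randomised equally to six arms (protocol 5.2 and 10.3), so 600 / 6 = 100.
- k, the never-dosed participants in an arm: not given in the documents. I assume 1 to 5 for illustration; 0 is also possible.
- p, the event rate among the dosed: 20%, for illustration.

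If the never-dosed contribute no counted events, the reported percentage is p × (100 − k) / 100.

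| k | Multiplier | 20% is shown as |
|---|---|---|
| 0 | 1.00 | 20.0% |
| 1 | 0.99 | 19.8% |
| 2 | 0.98 | 19.6% |
| 3 | 0.97 | 19.4% |
| 5 | 0.95 | 19.0% |

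**Comparison with placebo.** With a true risk ratio of 1.00:

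- Three never-dosed in an active arm and none on placebo: 0.97 / 1.00 = 0.97.
- Three on placebo and none in the active arm: 1.00 / 0.97 = 1.03.
- Equal numbers in both arms: the ratio does not change.

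**Direction within an arm.** Protocol 9.2.1 collects adverse events from the start of Visit 3, the randomisation visit, and not from the first dose. SAP 14.4.1.3 phases events by treatment start and stop dates, which a never-dosed person lacks, and its note makes on-treatment the default when nothing shows otherwise. With k = 1, p = 20% and one such event counted, the arm shows (0.20 × 99 + 1) / 100 = 20.8%, which is above 20%. Dilution is the usual result but not a certain one.

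**What is not touched.** Change-from-baseline summaries and the spirometry model at Days 84 and 168 use only participants with measurements at those visits. The per protocol population is drawn from mITT and inherits the wording, but the primary analysis needs at least 10 diary days in Month 6, counted from the first dose (SAP 14.6.1 and 14.6.3). A never-dosed person cannot supply these. PK membership needs a sample taken on danirixin (SAP 4.2).

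**The case against.** The best defence is that the SAP, read as a whole, means a dosed population. It repeats the protocol's presumption of dosing, and it describes the safety and spirometry estimands, and the supportive analyses of randomised treatment in 7.1.3 and 7.2, as covering dosed participants. That is good evidence of intent. It does not supply the condition. In protocol 10.4 the presumption interprets an explicit dose requirement. In SAP 4.1 the only requirement it can act on is the randomised-in-error exclusion, and the SAP states no consequence for someone else who is shown not to have been dosed.

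The second defence is that the group is probably almost empty. Randomisation and first dispensing are both at Visit 3, with pre-dose PK samples and a pre-dose ECG that day, and the screen or run-in failure route is already closed. This stands, and it limits the importance of the point.

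A reader might also infer four stronger things that the documents do not support:

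- **That the safety denominators do contain unexposed people.** No count is given, so this is only a possibility.
- **That every safety table is affected.** Most use mITT, but Tables 3.6 and 3.10 use all subjects, and measurement-based summaries do not gain members.
- **That the bias always favours danirixin or always lowers rates.** The on-treatment default and the placebo-arm case above show otherwise.
- **That a never-dosed participant cannot be placed in an arm.** The SAP leaves the randomised arm only when a different treatment was taken, so the natural default is the randomised arm, although the SAP does not say so.

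**Conclusion.** The inconsistency is real and undeclared. The operative SAP definition of mITT is wider than protocol 10.4 and wider than the SAP's own safety estimand, by exactly the participants who were validly randomised, were not screen or run-in failures and were never dosed. Its likely effect is minor: about 1% relative per such participant in an arm of 100, usually downward, on mITT-based adverse event percentages, and nothing if there are none. That size rests on an assumed k and on no events being counted in those participants. The primary efficacy conclusion is not at risk. This is a correction worth making because it is cheap, not because it threatens the trial's results.

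**What to change.** In the mITT row of SAP 4.1, add the condition that the participant received at least one dose of study treatment. Keep reporting by actual treatment, and keep the presumption that randomised participants were dosed unless it is clearly disproved. If the wider set is in fact wanted, declare and justify it in Table 1 and reword SAP 8 and 8.4 to match.

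Report randomised but never-dosed participants in disposition only. Table 1.1 is itself run on mITT, so the place for them is Table 1.10, which uses all subjects and already counts randomised and mITT participants. Give them their own line there, so that they are not mixed with those randomised in error.

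The cost is one phrase in the SAP, one condition in the population flag and one line in an existing table. No new data are needed.

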## 4.3. Protocol Deviations

Protocol Deviations (PDs) will be tracked by the study team throughout the conduct of the study in accordance with the Protocol Deviation Management Plan (6JUL2018, V2.0):

- Data will be reviewed prior to SDL to ensure all important deviations are captured and categorised on the protocol deviations dataset.
- Participants who received an incorrect treatment container will be captured as an important protocol deviation. Whether or not the incorrect container contained incorrect treatment will be identified following DBF in the analysis dataset and the PD will be flagged accordingly.
- This dataset will be the basis for the summaries and listings of protocol deviations.
- Important protocol deviations (including deviations related to study inclusion/exclusion criteria, conduct of the trial, participant management or participant assessment) will be summarised and listed.
- A separate summary and listing of all inclusion/exclusion criteria deviations will also be provided. This summary will be based on data as recorded on the inclusion/exclusion page of the electronic case report form (eCRF).

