### 7.1. Primary Efficacy Analyses

#### 7.1.1. Month 6 E-RS: COPD Total Score Dose-Response Analysis

The estimand is the effect of actual treatment in the population of participants who did not experience a protocol deviation considered to impact efficacy and completed six months of treatment.

A Bayesian dose response model will be applied to the change from baseline to Month 6 and used to estimate the treatment difference between placebo and each dose.

The dose-response model will be fitted using Bayesian techniques with non-informative priors for E0 and Emax and a functional uniform prior (FUP) for ED50 and the slope parameter, m ([Bornkamp, 2014](#)). The rationale for this choice of inference is that the FUP shrinks the dose-response towards a flat line throughout the dose range, therefore providing more conservative estimates of the dose-response relationship compared to maximum likelihood.

For the strategic interim, the posterior predictive probability of success (PPS) at the end of the study will be calculated for each dose using the formula suggested by Spiegelhalter et al. ([Spiegelhalter, 2004](#)) as follows:

$$PPS = \Phi \left[ \frac{\sqrt{(m+n)} \frac{(-my_m)}{\sigma_{trt\ diff}} + \sqrt{\frac{m}{n}} z_{0.9}}{\sqrt{mn}} \right]$$

Where m is the average number of participants with Month 6 data in the placebo and comparative dose arm, n is the average number of participants yet to be observed (assuming 90% of participants, rounded to the nearest integer, in each treatment group will provide month 6 data at end of study. If the actual number of participants at month 6 exceeds this, the actual number will be used),  $y_m$  is the posterior mean difference from the fitted model, and  $\sigma_{trt\ diff}$  is the standard deviation (SD) of the posterior mean difference.

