## 14. APPENDICES

### 14.1. Appendix 1: Protocol Deviation Management and Definitions for Per Protocol Population

#### 14.1.1. Exclusions from Per Protocol Population

A participant meeting any of the following criteria will be excluded from the Per Protocol population:

Number	Exclusion Description
01	Inclusion #2 – FEV1/FVC ratio $\geq 0.70$ or % predicted FEV1 $< 40\%$ at Screening
02	Inclusion #4 – $< 2$ historical exacerbations or one historical exacerbation with screening fibrinogen $< 3$ g/L
03	Inclusion #5 - Smoking history of $< 10$ pack years at Screening
04	Exclusion #4 - Screening visit is less than 14 days since the completion of a course of antibiotics or oral steroids for a COPD exacerbation
05	Exclusion #14 - Use of PDE4 inhibitors within 30 days of Screening
06	Exclusion #26 - Oxygen use that is not PRN at Screening

At the strategic interim a participant meeting any of the following criteria will be excluded from the Per Protocol population:

Number	Exclusion Description
07	Xanthines at any time between the day after screening and end of treatment
08	PDE4 inhibitors at any time between screening and end of treatment
09	Chronic use (more than 3 months) of erythromycin or azithromycin for between screening and end of treatment
10	Participants who stopped study medication for more than 14 days
11	Blind broken

For the final analysis a participant meeting any of the following criteria will have data excluded from the time of the deviation. If a prohibited medication is taken prior to randomisation the participant will be excluded from the Per Protocol population.

Number	Exclusion Description
07	Xanthines at any time between the day after screening and end of treatment
08	PDE4 inhibitors at any time between screening and end of treatment
09	Chronic use (more than 3 months) of erythromycin or azithromycin between screening and end of treatment
10	Participants who stopped study medication for more than 14 days will be excluded from the PP analyses from the time they stopped taking study medication.
11	Data excluded from date of breaking of blind.

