Medical Conditions and Concomitant Medications
Cardiovascular Risk Factors

 
• Subjects with at least one of the following current or past medical conditions at Screening will be classed as having cardiovascular (CV) risk factor at screening. The number of CV risk factors at Screening (0, 1, or >=2) will be derived.                             
 
○ Coronary artery disease
 
○ Myocardial infarction
 
○ Arrhythmia
 
○ Congestive heart failure
 
○ Hypertension
 
○ Cerebrovascular accident
 
○ Hypercholesterolemia
 
○ Diabetes mellitus
 
 
 

Compliance
Treatment Compliance

Compliance= (tablets issued–tablets returned) x 100 / 2 x (treatment stop date – treatment start date +1)
 
If any count of tablets returned is missing overall compliance will be set to missing.
 
 
• Compliance will be categorized as follows:                             
 
< 80 %
 
≥ 80 % to < 95 %
 
≥ 95 % to ≤105 %
 
>105 % to ≤120 %
 
>120 %
 
 
 
• If a participant received a treatment other than the randomized treatment during the study, the compliance will still be calculated using data from all containers received and overall treatment start and stop dates.
 

Daily Diary Compliance

Overall compliance= (number of days with non-missing data between study treatment start and the earliest of (Study day 168 and day before study treatment stop)) x 100 / (Earliest of (Study day 168 and day before study treatment stop date) – treatment start date +1)
 
 
• Overall compliance will be categorized as follows:                             
 
< 50 %
 
≥ 50 % to < 60 %
 
≥ 60 % to < 70 %
 
≥ 70 % to < 80 %
 
≥ 80 % to < 90 %
 
≥ 90 % to ≤100 %
 
 
 
 
Baseline and Monthly compliance= number of days with non-missing data between periods defined in Section 14.6.3
 
 
• Baseline compliance will be categorized as follows: Number of days completed <4, ≥4
 
• Monthly compliance will be categorized as follows: Number of days completed <10, 10-20, >20
 

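### The final per-protocol rules do not remove Month 6 E-RS data collected on a treatment other than the one the participant is analysed under, so a wrong-strength bottle at Visit 9 enters the dose-response fit at a dose not taken

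*SAP*

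**What the plan says.** SAP 4.1 defines PP as "All participants from the mITT population who did not have a protocol deviation considered to impact efficacy". PP has no rule of its own for choosing the treatment label. The mITT rule, in SAP 4.1 and Protocol 10.4, is conditional: "If any subject received more than one treatment during a treatment period", then "their data will be reported according to the treatment they received for the longest period of time". SAP 4.2 carries these definitions forward: "The final analysis will use the same populations as above, plus additional populations as defined below".

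The primary analysis is described in SAP 7.1.1 this way: "The estimand is the effect of actual treatment in the population of participants who did not experience a protocol deviation considered to impact efficacy". SAP 7.1.1.4 cuts Month 6 data only from the point of such a deviation, and refers to Appendix 1 (SAP 14.1.1) for what counts as one.

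That appendix has eleven rows. Rows 01 to 06 are eligibility failures. Rows 07 to 11 are xanthines, PDE4 inhibitors, chronic macrolide use, a long treatment gap and a broken blind. Row 10 in the final-analysis list begins "Participants who stopped study medication for more than 14 days will be excluded from the PP analyses".

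The SAP foresees dispensing errors. Section 4.3 says "Participants who received an incorrect treatment container will be captured as an important protocol deviation", and adds that whether the contents were actually wrong is established after database freeze and flagged. The compliance rule in 14.6.2 covers the case "If a participant received a treatment other than the randomized treatment during the study", and counts all containers. Listing 38 lists misallocations. None of these removes or relabels efficacy data.

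**The concern.** The label follows the longest exposure over 24 weeks, but the primary endpoint is measured in the last four. The two can differ, and the last bottle supplies almost exactly the endpoint window. A Month 6 score recorded on one strength, or on placebo, would then enter the dose-response model at another dose.

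The list is also uneven. A danirixin participant who stops treatment for more than 14 days has later data cut. One who takes placebo tablets for four weeks by mistake is off danirixin for longer, yet stays in at the active dose.

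Timing makes prespecification worthwhile. SAP 3.2 unblinds the datasets before database freeze, and SAP 4.3 identifies incorrect treatment only after it. If the flag is meant to lead to exclusion, the SAP does not say so. Deciding case by case at that stage would mean choosing who leaves the primary analysis with treatment known.

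Safety tables use the same label, so an event that begins on a wrong bottle is counted under the arm of longest exposure.

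**Working it through.** **Inputs**
- Dispensing at Visits 3, 5, 6, 7, 8 and 9, nominal Days 1, 28, 56, 84, 112 and 140; Visit 9 window ±3 days (Protocol Table 1).
- Treatment for 168 days; Month 6 is days 141 to 168, with at least 10 diary days required (Protocol 10.5.1.1; SAP 14.6.3).
- SD 6.5; Scenario 1 means of 0, -0.5, -1, -2, -2.5 and -3 for placebo, 5, 10, 25, 35 and 50 mg (Protocol 10.2, Table 4).
- About 540 completers in six equal arms: 540/6 = 90 per arm (Protocol 5.2 and 10.3).

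**The plan's own figure.** Protocol 10.2 reports that, at n = 600, more than 80% of simulations exclude zero for 35 mg versus placebo in every scenario. A simple pairwise comparison (100 per arm, two-sided 10%) gives 0.859, 0.567 and 0.702 for Scenarios 1 to 3, so it does not reproduce this. An approximate Bayesian three-parameter Emax fit gives 0.987, 0.820 and 0.900, which agrees. The inputs are therefore read as intended. The present point does not depend on that figure.

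**Days per bottle.** Nominal supply is 27 + 28 + 28 + 28 + 28 + 29 = 168 days.

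| Single wrong bottle at | Days on wrong treatment | Days on original | Wrong days in Month 6 |
|---|---|---|---|
| Visit 3 | 27 | 141 | 0 |
| Visits 5, 6, 7 or 8 | 28 | 140 | 0 |
| Visit 9 | 29 | 139 | 28 of 28 |

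In a completer the label stays with the original treatment in every row. Only the Visit 9 bottle reaches Month 6.

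**Visit window.** With Visit 9 on Day 137 or 140, all 28 days are affected. On Day 143 the count is 26 if the new bottle is started that day and 25 if the next day. Leftover tablets could lower it further; the quantity dispensed is not given.

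**Reverse error.** Wrong bottles for most of the study and the right one at Visit 9 put a Month 6 value from the original dose under the wrong label.

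**Size.** The shift in an arm mean is k × |difference between the two treatments| / 90 for k participants, assuming the switched treatment has its full effect at once.
- Largest contrast, placebo versus 50 mg: 3/90 = 0.033 for k = 1, 9/90 = 0.10 for k = 3, 15/90 = 0.167 for k = 5.
- Average contrast over the 15 pairs of arms: 22/15 = 1.47, so 1.47/90 = 0.016 per case.
- Yardstick: pairwise 90% half-width = 1.645 × 6.5 × √(2/90) = 1.59. One worst case is 0.033/1.59 = 2% of it; five are 0.167/1.59 = 10%.

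The values of k are assumed.

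**Direction.** A placebo participant given 50 mg moves placebo toward 50 mg. A 5 mg participant given 50 mg moves the 5 mg mean by (-3 + 0.5)/90 = -0.028, which widens its difference from placebo.

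**Effect of excluding only the wrong-treatment days.** For a wrong Visit 9 bottle, 0 of 28 days remain if the visit is on or before Day 140, and 2 to 3 if it is on Day 143. Both are below 10, so Month 6 becomes missing. After a wrong bottle at Visit 3, 5, 6, 7 or 8 on nominal dates, all 28 Month 6 days remain.

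**The case against.** The strongest reply is that the numerical effect is negligible: no error rate is given, and one worst case is about 2% of a pairwise half-width. That stands. Labelling by longest exposure is also a prespecified convention in both documents, and nothing here asks for time-varying assignment. It is fair too that PP's use of the mITT label is inferred from how PP is built. If PP does not inherit the label, it has no rule at all. The Protocol Deviation Management Plan, which might give the 4.3 flag a consequence, is not among the documents, so its intent cannot be checked.

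A reader might go further in several ways that the documents do not support:
- That one wrong bottle can never be the longest treatment. This holds for completers only. Someone given a wrong bottle at Visit 3 who withdraws before Day 28 took nothing else.
- That errors always pull toward no difference. The 5 mg example above goes the other way.
- That all data after a wrong container should be cut, as rows 10 and 11 do. This would delete valid Month 6 values after an error at any of the first five dispensing visits.
- That adverse events should move to the arm of the treatment at onset. The event would then sit in an arm whose denominator does not contain that participant.

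**Conclusion.** The gap is real and narrow. For a completer with a wrong-strength bottle at Visit 9, the stated rules place that participant's Month 6 value, wholly or nearly so, at a dose not taken, against the SAP's own estimand. It concerns individual values, not the trial's primary endpoint as a whole.

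Each case moves an arm mean by at most 0.033 points under Scenario 1 with about 90 completers per arm, and the direction depends on the exchange. Conclusions are unlikely to change unless misallocation is common, which the documents do not allow anyone to judge. The case for acting rests on the estimand, on consistency with row 10, and on settling the rule before treatment is known. It assumes that PP inherits the mITT label and that the Visit 9 bottle is used when dispensed.

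**What to change.** Add a row to the final-analysis list in SAP 14.1.1: *Confirmed receipt of a treatment different from the one under which the participant is analysed: efficacy data collected during the wrong-treatment period are excluded.* Then apply the 10-day minimum to the remaining Month 6 days.

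This wording also catches the reverse error. It leaves alone wrong containers that held the correct strength, and participants who took one wrong treatment throughout and are analysed under it.

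For safety, keep the mITT arm rule and list adverse events with onset during a wrong-treatment period, showing both treatments. Listings 5, 16 and 38 already hold most of the information, but across separate displays.

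The cost is one SAP row, one short listing, and programming on a flag that 4.3 already plans. A few participants lose E-RS data for the affected months, and those with a wrong Visit 9 bottle leave the Month 6 dose-response analysis.
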